Sample size will be based on power considerations for the parent clinical trial. All analyses will utilize an intention-to-treat approach. Data confirmed to be missing at random will be addressed as appropriate using multiple imputation.⁹⁷ We will first directly compare mean cost between the study groups using generalized linear modeling to account for the typically right skewed cost data distribution.^{98,99} We will then calculate the incremental cost-effectiveness ratio, defined as the difference in mean cost per patient in the high and low transfusion threshold arms divided by the difference in the mean effect between the study arms. The outcome will thus be expressed as the cost per survivor without neurodevelopmental impairment. To assess statistical uncertainty in the joint distribution of costs and effects, we will use nonparametric bootstrapping and report results as cost-effectiveness acceptability curves.^{100,101,102,103} Finally, we will assess uncertainty in parameter values by using sensitivity analysis, in which we will recalculate the cost-effectiveness after varying the input values for certain variables through a plausible range.

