4.0 Specific Aims

4.1 Specific Aim 1

To examine whether the clinically relevant composite primary outcome of death or significant neurodevelopmental impairment in survivors at 22-26 months of corrected age is less common among preterm infants who, by transfusion practice, are maintained at higher hemoglobins. Neurodevelopmental assessments will be performed by trained and annually recertified examiners, who are masked to treatment allocation, using standardized tools: the Bayley Scales of Infant Development-III (BSID-III) and the Gross Motor Function Classification Scale (GMFCS).^{125,126} The primary outcome consists of any one of the following: (i) Cognitive delay where delay is defined as BSID-III cognitive score < 85 (>1 standard deviation below the mean). (ii) Cerebral Palsy if the child has a non-progressive motor impairment characterized by abnormal muscle tone and impaired range or control of movements. Moderate cerebral palsy (CP) is defined as level II or III on the GMFCS. Severe or non-ambulatory CP consists of GMFCS IV or V. (iii) Severe vision impairment, defined as corrected visual acuity in the better eye less than 20/200, determined by pediatric ophthalmologists. (iv) Severe hearing impairment, defined as bilateral hearing loss requiring amplification or cochlear implant. (v) Death before 22-26 month follow-up assessment. The primary outcome is deemed present if one or more of the individual components of the composite outcome are present, or absent if no component was present. If no component is present, one or more missing components render the primary outcome to be deemed missing.

4.2 Specific Aim 2

We will examine in which arm the following secondary outcomes are more common:

Short term, to NICU discharge:

- (a) Survival to discharge without severe morbidity, defined as any of the following: bronchopulmonary dysplasia, retinopathy of prematurity (stage ≥ 3 or requiring treatment), or serious brain abnormality (grade 3 or 4 intraventricular hemorrhage, periventricular leukomalacia, or ventriculomegaly).
- (b) Weight, length, and head circumference at 36 weeks postmenstrual age or at discharge from NICU, whichever occurs first.
- (c) Serious abnormality on cranial ultrasound examination: grade 3 or 4 intraventricular hemorrhage, periventricular leukomalacia, or ventriculomegaly;
- (d) Age at final tracheal extubation; age at final caffeine dose

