6.6 Choice of Primary Outcome

We will use a composite outcome of death or significant neurodevelopmental impairment in survivors at 22-26 months of corrected age. Children will be assessed at 22-26 months of corrected age by staff unaware of assignment. Centers will schedule visits as early as possible within this window. Outcome assessments will be conducted by physicians or nurses specializing in neonatal follow-up examination and certified psychologists. Neurodevelopmental Impairment will be defined in this study, as one or more of the following: cognitive delay, moderate or severe cerebral palsy, or severe visual or hearing impairment, as defined below.

Cognitive delay will be assessed by certified psychologists will assess infants using the Bayley Scales of Infant Development III (BSID-III). Cognitive delay is defined as BSID-III cognitive score < 85 (>1 standard deviation below the mean).

Cerebral Palsy is diagnosed if the child has a non-progressive motor impairment characterized by abnormal muscle tone and impaired range or control of movements. Medical history, physical examination and neurological examinations will be used to determine the presence of moderate or severe cerebral palsy (CP). Moderate CP is defined as level II or III on the Gross Motor Function Classification Scale (GMFCS).^{125,126} Severe or non-ambulatory CP consists of GMFCS IV or V.

Severe vision impairment; is defined as corrected visual acuity in the better eye less than 20/200 determined by pediatric ophthalmologists.

Severe hearing impairment, is defined as bilateral hearing loss requiring amplification or the insertion of a cochlear implant as determined by a sound field hearing assessment or auditory brainstem responses.

The primary outcome will be deemed present if one or more of the individual components of the composite outcome are known to be present, or absent if no component was present. If no component was present, one or more missing components will cause the primary outcome to be deemed missing.

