6.10 Analysis Plan

Main Study: All analyses will be conducted on an intention-to-treat basis, with the caveat that infants surviving to discharge, but lost to follow-up at 22-26 months, will be excluded from the primary analysis and considered ignorably missing. We will, however, assess the impact of outcomes lost to follow-up on our results by performing sensitivity analyses that assume all positive or all negative outcomes for those with missing data. We will also conduct bivariate analyses to compare the in-hospital characteristics of children lost to follow-up versus those with assessment of the primary outcome. Note that, based on previous NRN trials in similar populations, we expect the follow-up rate among survivors to be above 90%.

All analyses will be adjusted for design effects: stratification by center and birth weight group. The primary outcome of death or NDI at 22-26 months adjusted age will be analyzed using robust Poisson regression. Adjusted relative risks and 95% confidence intervals will be reported. Secondary analyses of the primary outcome may adjust for additional baseline covariates such as SNAPPE scores at NICU admission and socioeconomic status..

The consistency of the treatment effect over birth weight strata and gender, and treatment heterogeneity across the different centers, will be investigated.

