Although the sample size calculations described above were based on the primary outcome, we will have 80% power with a two-tailed alpha of 0.05 to detect the following differences in important secondary outcomes (rates in the low threshold group are based on findings of the PINT trial): any transfusion 89.0% in the low threshold group (LOW) vs. 92.9% in the high group (HI); NEC 8.5% in LOW vs. 5.0% in HI; brain injury (PVL, echodense lesions or ventriculomegaly) on latest ultrasound (US) to 36 weeks 18.5% in LOW vs. 24.6% in HI; death before discharge 21.5% in LOW vs. 16.1% in HI; combined death, severe ROP, BPD, or US brain injury 74.0% in LOW vs. 67.7% in HI.

Analysis All analyses will be conducted on an intention-to-treat basis, with the caveat that infants surviving to discharge, but lost to follow-up at 22-26 months, will be excluded from the primary analysis and considered irrevocably missing. We will, however, assess the impact of outcomes lost to follow-up on our results by performing sensitivity analyses that assume all positive or all negative outcomes for those with missing data. We will also conduct bivariate analyses to compare the in-hospital characteristics of children lost to follow-up versus those with

assessment of the primary outcome. Note that, based on previous NRN trials in similar populations, we expect the follow-up rate among survivors to be above 90%.

All analyses will be adjusted for design effects: stratification by center and birth weight group. The primary outcome of death or NDI at 22-26 months adjusted age will be analyzed using robust Poisson regression. Adjusted relative risks and 95% confidence intervals will be reported. Secondary analyses of the primary outcome may adjust for additional baseline covariates such as SNAPPE scores at NICU admission and socioeconomic status. The consistency of the treatment effect over birth weight strata and gender, and treatment heterogeneity across the different centers, will be investigated.

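### The composite scoring rule keeps a partly assessed survivor only if an impairment was found, which raises the analysed death-or-NDI rate in both arms; the primary analysis does not use the components that were observed

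*Combined protocol and SAP*

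**What the plan says.** Section 6.6 sets the scoring rule in two halves. First: "The primary outcome will be deemed present if one or more of the individual components of the composite outcome are known to be present". Second: "If no component was present, one or more missing components will cause the primary outcome to be deemed missing". Section 4.1 repeats the second half in nearly the same words: "If no component is present, one or more missing components render the primary outcome to be deemed missing".

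For a survivor, the components come from different assessments: a psychologist's Bayley III, a neurological examination with GMFCS level, a sound-field or brainstem hearing test, and vision, defined as "corrected visual acuity in the better eye less than 20/200 determined by pediatric ophthalmologists".

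Section 6.10 analyses the composite by robust Poisson regression adjusted for centre and birth weight group. Infants who survive to discharge but are lost to follow-up "will be excluded from the primary analysis and considered ignorably missing". The corresponding sentence in Appendix A (item 6, data analysis plan) reads "will be excluded from the primary analysis and considered irrevocably missing". Both places add sensitivity analyses that set missing outcomes to all positive or all negative, and a comparison of in-hospital characteristics of "children lost to follow-up versus those with assessment of the primary outcome". Partly assessed children have no category of their own. Multiple imputation appears only for the economic evaluation, in section 3.2: "Data confirmed to be missing at random will be addressed as appropriate using multiple imputation".

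**The concern.** Take two children who both attend and both lack only the acuity measurement. One has a cognitive score of 80 and is scored present. The other has a score of 100, no cerebral palsy and normal hearing, and is scored missing. Among partly assessed survivors, every child who is counted is an event, and every child who is dropped had no impairment found. Whether the composite is missing therefore depends on the components that were observed, and the available-case primary analysis does not condition on them.

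At stake are the reported death-or-NDI rates in each arm and, if partial assessment were more common in one arm, the treatment comparison itself. Partial assessment is foreseeable: a survivor needs several separate assessments, and the rule exists because some will be missing.

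**Working it through.** **The plan's own figure.** Section 6.9 assumes 53.5% v 46.5%, two-sided alpha 0.05 and 80% power, and obtains 1,658.
- Uncorrected: n = [1.960 × √(2 × 0.5 × 0.5) + 0.842 × √(2 × 0.535 × 0.465)]² / 0.07² = 799.7, so 800 per arm.
- With continuity correction: n/4 × [1 + √(1 + 4/(0.07n))]² = 828.05, so 829 per arm, or 1,658 in total.
- 1,658 × 1.10 = 1,823.8, so 1,824.

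The figure reproduces, and this point does not change it.

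**Direction of the effect.** Let *s* be the share of impaired, partly assessed survivors whose impairment shows in an assessed component. Among partly assessed survivors, P(missing | unimpaired) = 1 and P(missing | impaired) = 1 − *s*, which is below 1 whenever *s* > 0.

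**Size with equal arms.** The documents give no partial-assessment rate, so these inputs are assumptions: 20% deaths; 37.5% impairment among survivors, giving a true composite of 0.20 + 0.80 × 0.375 = 50.0%; 5% of survivors wholly unassessed; a share *m* of survivors partly assessed, lacking only a component that does not decide the outcome (*s* = 1).

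As fractions of an arm:
- Events analysed = 0.20 + 0.80 × 0.95 × 0.375 = 0.485, whatever *m* is.
- Number analysed = 0.96 − 0.80 × *m* × 0.625.

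| *m* | Number analysed | Analysed rate |
|---|---|---|
| 0% | 0.960 | 50.5% |
| 3% | 0.945 | 51.3% |
| 5% | 0.935 | 51.9% |
| 8% | 0.920 | 52.7% |
| 10% | 0.910 | 53.3% |

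At *m* = 5% the rise over no partial assessments is 51.87 − 50.52 = 1.35 points.

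**Effect on the contrast, equal partial rates.** Take the plan's 53.5% v 46.5% and split off deaths at the 21.5% and 16.1% before discharge in section 6.9, with no wholly lost children. With *p* the event rate and *d* the death rate:

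analysed rate = E / [E + (1 − *p*)(1 − *m*)], where E = *d* + (*p* − *d*)(1 − *m*) + (*p* − *d*)*ms*.

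- At *m* = 5%, *s* = 0.9: low 0.5334/0.97515 = 54.7%; high 0.4635/0.97173 = 47.7%; relative risk 0.872 against a true 0.465/0.535 = 0.869.
- Over *m* = 2–10% and *s* = 0.3–0.9: relative risk 0.870–0.875, risk difference 7.0–7.1 points.
- With 50% events in both arms and equal *m*: difference zero, type I error 5.0%.

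**Effect on the contrast, unequal partial rates, no true effect.** In the first model:
- 10% v 5%: 53.30 − 51.87 = 1.4 points
- 8% v 4%: 52.72 − 51.60 = 1.1 points
- 6% v 3%: 52.15 − 51.32 = 0.8 points

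These are 12–20% of the 7-point target. In the second model (50% events, 18.8% deaths, *s* = 0.3–0.9), 3% v 8% gives 0.8–1.2 points and type I error of 6.2–8.2%.

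**What the planned extreme-case analyses do, if they include these children.** In the first model, all-negative gives 0.485/1 = 48.5% in each arm whatever *m* is, so the spurious difference vanishes. The level falls below the true 50.0% because wholly lost impaired children are scored unimpaired (0.04 × 0.375 = 1.5 points). All-positive at *m* = 5% gives 0.485 + 0.065 = 55.0%; at *m* = 10% it gives 0.485 + 0.090 = 57.5%. For 10% v 5% it therefore widens the spurious difference to 2.5 points.

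**The case against.** The strongest reply is that the plan already covers this. Under section 6.6 these children's outcome is deemed missing, and the all-positive and all-negative analyses are for those with missing data. On that reading the problem is bounded, and the all-negative analysis removes the spurious difference exactly in the model above. This stands in large part. But the sentence opens with outcomes lost to follow-up, so coverage of children who attended should be stated. The analyses also give an attended, mostly unimpaired child the same value as a wholly lost one, and they leave the main estimate as it is.

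A second reply is that the reported result is a relative risk, which hardly moves with equal partial rates. That is correct. Examiners are masked (section 6.4) and the transfusion algorithm ends at 36 weeks postmenstrual age or discharge (section 6.2), long before the visit. Families and caregivers are not masked, so unequal rates are not excluded, but nothing points to them. The 10% case is also high: 5% + 10% × 0.625 = 11.25% of survivors would lack a primary outcome, against expected follow-up above 90%.

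A reader might infer three stronger claims that the documents do not support:
- *That the plan declares these children ignorably missing.* The phrase in section 6.10 is about infants lost to follow-up; extending it to partly assessed children is an inference. Nor is ignorability impossible: given the observed components, the composite may be missing at random. The defect is that the analysis does not condition on them.
- *That their Bayley and neurological data are thrown away.* Sections 4.2, 6.6 and 6.7 analyse each component as a secondary outcome. The data go unused only for the composite.
- *That the cost per unimpaired survivor carries the same error.* Section 3.2 provides for multiple imputation there, so this is not established.

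**Conclusion.** The point holds as a worthwhile, inexpensive improvement. The rule makes missingness of the composite depend on the observed components, and the available-case primary analysis ignores them. The analysed rate rises in both arms, by about 1.4 points at 5% partly assessed under the stated assumptions.

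It should not be read as showing that the treatment comparison is biased. With equal partial rates the relative risk is nearly unchanged and there is no bias under the null. The 0.8 to 1.4 point differences are conditional on partial rates that differ by arm. All sizes rest on assumed partial rates, and the first model assumes that the missing component never decides the outcome. A child impaired only in an unassessed component is also dropped, so the dropped group is mostly, not wholly, unimpaired. At *m* = 5% and *s* = 0.9, about 94% of those dropped are unimpaired; at *s* = 0.6, about 80%.

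**What to change.** Keep the composite definition and change only its handling when components are missing:

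1. For survivors with some components observed, multiply impute the missing components within arm. Use the observed Bayley, GMFCS and sensory findings, in-hospital morbidities, birth weight group and centre. Then derive the composite and fit the planned model.
2. Report the present scoring rule as a sensitivity analysis.
3. State that the all-positive and all-negative analyses include partly assessed children.
4. Tabulate partly assessed children by arm and by missing component.
5. Reconcile the wording on lost infants between section 6.10 and Appendix A, and say whether it applies to partly assessed children.

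The cost is plan wording and modest programming, with no new visits, data or patients. The downside is reliance on a missing-at-random imputation model. Its form should be fixed before unblinding, because severe sensory impairment is likely to be sparse within arm and centre.

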6.7 Main secondary Outcomes

Secondary outcomes are measured at two time points:

- (A) During initial hospitalization: (i) Ultrasound grade 3 or 4 IVH, cystic PVL, or ventriculomegaly; (ii) Bell stage 2 or 3 NEC; (iii) Apnea mandating either caffeine or respiratory support; (iv) Age at final tracheal extubation; (v) Number of donor exposures by RBC donors or other blood product; (vi) Number of transfusions; (vii) ROP stage 3 or greater or requiring treatment; (viii) Time to regain birth weight; (ix) Time to full feedings; (x) Death before discharge; (xi) BPD at 36 weeks postmenstrual age based on need for oxygen supplementation following an oxygen reduction test; (xii) Decreased height, weight, or head circumference at 36 weeks postmenstrual age; (xiii) length of hospital stay at Level 3 care; and (xiv) Costs of hospitalization.
- (B) At 22-26 months corrected age, each of the composite outcomes individually: (i) Moderate or severe cerebral palsy; (ii) Severe vision impairment; (iii) Severe hearing impairment; (iv) BSID-III Cognitive score < 85; (v) BSID-III cognitive, language, or motor score <70; (vi) Gross Motor Function level \geq II; (vii) CBCL Internalizing, Externalizing, and Total Problems aggregate T scores of \geq 64 (clinical range) and 60-63 (borderline range) will be evaluated. (viii) Death before 22-26 month follow-up; (ix) Decreased height, weight, or head circumference at 22-26 month assessment; and (x) Cost-benefit analysis of primary outcome at 22-26 months.

Analyses of all primary and secondary outcomes will be adjusted for the design effects of stratification by center and birth weight group, and correlation between multiple births.

6.8 Potential Confounders and Strategy to Limit their Impact

- (i) Severity of initial illness: Randomization should achieve balance at baseline. Adjustment for the SNAPPE score¹³⁸ on admission to NICU will be performed *post-hoc* if imbalances arise.
- (ii) Blood bank practices: Center stratification will ensure balance across study.
- (iii) Gender of blood donor: A retrospective cohort study of infants with birth weight <1500 g suggested that transfusion from male donors is associated with an increase in rate of NEC.⁶⁴ Thus, the proportion or total volume of transfused blood from male donors will be covariates in the model to predict NEC. This will be collected while preserving HIPPA anonymity, after the main trial is complete. This will be done by only using the blood unit ID number. This will be relayed to the issuing blood banks, who would provide only the gender of the donor to the investigators.
- (iv) Sociological determinants: Home environmental influences and potential enhanced neurodevelopmental programs will be recorded as highest maternal educational levels, at enrollment. Adjustment for these will be conducted in secondary analyses.

6.9 Statistical Design Considerations

The primary objective of the TOP trial is to assess the difference in the primary outcome of survival without significant NDI (or, equivalently, death or NDI) at 22-26 months adjusted age in the two treatment arms. This outcome is similar to that used in the PINT trial, which found rates of death or neurosensory impairment at 18 months of 45.2% in the low trigger group and 38.5% in the high trigger group. Based on these findings, we believe that an absolute difference of 7% is the minimal clinically significant difference we would wish to detect in the rate of death or NDI. We considered several other factors in estimating the sample size for this study. First, we calculated the rate of death or NDI among infants born at NRN centers in 2005-2008 with GA 22-26 weeks and birth weight <1000 g who survived to 12 hours, which was 52%. However, we recognized that this population differed somewhat from that of the TOP trial, which proposes to enroll infants less than 29 weeks GA. In addition, the current NRN definition of NDI incorporates only the cognitive composite score of the Bayley III, while future definitions will likely also involve the Bayley III motor scales which have been collected in the Network only since January 2010. Thus, we recognized the limitations of estimating our sample size based only on current NRN data. At the same time, however, we were aware that the most conservative sample size estimate would result from an event rate of 50%, which current NRN data indicated was not implausible in our population. This led us to choose a conservative estimate based on assumed outcome rates of 53.5% and 46.5% (i.e., centered around an overall event rate of 50%) in the two treatment groups. With a two-tailed alpha of 0.05 and 80% power, the initial sample size estimate was 1,658 infants. The sample size was additionally inflated by 10% to account for loss to follow up at 22-26 months, yielding a final sample size estimate of 1,824.

Although the sample size calculations described above were based on the primary outcome, we will have 80% power with a two-tailed alpha of 0.05 to detect the following differences in important secondary outcomes (rates in the low threshold group are based on findings of the PINT trial): any transfusion 89.0% in the low threshold group (LOW) vs. 92.9% in the high group (HI); NEC 8.5% in LOW vs. 5.0% in HI; brain injury (PVL, echodense lesions or ventriculomegaly) on latest ultrasound (US) or neuroimaging closest to 36 weeks 18.5% in LOW vs. 24.6% in HI; death before discharge 21.5% in LOW vs. 16.1% in HI; combined death, severe ROP, BPD, or US brain injury 74.0% in LOW vs. 67.7% in HI.

